### **Kaplan-Meier (KM) Analysis**

KM analysis will be used to estimate the time from the date of index procedure to the first CRBSI event and to determine the rate of freedom from CRBSI at 1-, 3-, 6-, and 12-months. CRBSI is considered as the event.

Subjects that have not reached CRBSI (event) will be censored or considered event free as described below.

- If the subject has experienced following events, subject will be censored at the earliest date of those events.
  - Catheter has been removed due to Kidney Transplant, Transferred to AVG/AVF, Peritoneal Dialysis, Withdrawal of Care, or Other reasons
  - Subject has discontinued from the study.

Note: How to assess the above events has been described in **Error! Reference source not found.** the Binary Analysis section.

- All the other subjects will be considered event free and will be censored on visit day (visit day can vary from lower limit to upper limit of visit window).

This endpoint will be evaluated on the mITT populations through 1-month, 3-months, 6-months, and 12-months.

### **5.3.2 Rate of freedom from Device and/or Procedure-related adverse events, at 1-month, 3-months, 6-months, and 12-months post-index procedure.**

#### **Binary Analysis**

Subject will be considered as having device and/or procedure-related adverse events for a given visit if the subject has experienced device and/or procedure-related adverse events prior to the upper limit of visit window for the visit:

- **AE CRF Page:** AE start date <= upper limit of the visit window AND (Relationship to Device: Is 'Related' or 'Likely Related' OR Relationship to Procedure: Is 'Related' or 'Likely Related') ; subject will be considered as a failure at the AE date

If the subject has not become failure and experience one of the following events prior to the lower limit of visit window, then subject will be considered as non-evaluable at the earliest occurrence of following event dates.

- Catheter has been removed due to Kidney Transplant, Transferred to AVG/AVF, Peritoneal Dialysis, Withdrawal of Care, or Other reasons
  - **Hemodialysis Catheter Re-Interventions CRF page:** *Catheter removal Equals Yes AND Reason for catheter removal Equals: Kidney Transplant, Transferred to AVG/AVF, Peritoneal Dialysis, Withdrawal of Care, or Other*

OR

- Subject has discontinued from the study.

If the subject has experienced any of the above non-evaluable events prior to the lower limit of visit window subject will be counted as a non-evaluable for a given visit. Else subject will be considered as a success (freedom from device and/or procedure-related adverse events) for a given visit.

The rate of freedom from device and/or procedure-related adverse events will be reported with 95% confidence interval from the exact binomial method. The analysis will be performed on the ITT population through 1-month, and mITT population through 1-month, 3-months, 6-months, and 12-months.

## KM Analysis

KM analysis will be used to estimate the time from the date of index procedure to the first device and/or procedure-related adverse event and to determine the rate of freedom from CRBSI at 1-, 3-, 6-, and 12-months. Device and/or procedure-related adverse event is considered as the event.

Subjects that have not reached device and/or procedure-related adverse event will be censored or considered event free as described below.

- If the subject has experienced following events, subject will be censored at the earliest date of those events.
  - Catheter has been removed due to Kidney Transplant, Transferred to AVG/AVF, Peritoneal Dialysis, Withdrawal of Care, or Other reasons
  - Subject has discontinued from the study.

Note: How to assess the above events has been described in **Error! Reference source not found.** the Binary Analysis section.

- All the other subjects will be considered event free and will be censored on visit day (visit day can vary from lower limit to upper limit of visit window).

This endpoint will be evaluated on the mITT population through 1-month, 3-months, 6-months, and 12-months. This endpoint may be evaluated for ITT population through 1-month.

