## 2.6 Study Procedure

Individuals that consent to participate in the study will be considered ***enrolled***. Participants that fail to meet eligibility criteria post-consent and prior to undergoing device placement with the study device will be considered ***screen failures***.

After the PI, or authorized designee(s), has determined that the participant is eligible for participation, the participant may be enrolled and undergo the Pristine™ Catheter placement procedure. Enrolled participants will continue clinical participation through the 12-month follow-up period. Participants into whom the Pristine™ Catheter was not introduced should be treated per SOC and the reason documented on the appropriate eCRF. Participation for these participants will end at time of the index procedure.

The study procedures and visit schedules for enrolled subjects is shown in Table 1.

Table 1. Schedule of Activities

Procedure	Screening	Index Procedure Day 1	Study Visits				
			Follow-Up Visit 1 1 month (±7-days)	Follow-Up Visit 2 3-months (±15-days)	Follow-Up Visit 3 6-months (±15-days)	Follow-Up Visit 4 12-months (±30-days)	Unscheduled
In-Clinic Visit or Telephone Visit (Screening must be in-clinic visit)	x	x	x	x	x	x	x
Informed Consent	x						
Eligibility	x						
Demographics	x						
Physical Examination	x						
Medical History	x						
Dialysis History	x						
Procedure Overview		x					
Study Device Details		x					
Hemodialysis Catheter Assessment			x	x	x	x	x
Dialysis Session Logs			x	x	x	x	x
Device Deficiencies / Malfunctions			←	→			
Re-Intervention Assessment			←	→			
Adverse Event Assessment			←	→			
Protocol Deviations			←	→			

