#### Infectious Complications

Complications due to any documented diagnosis of access infection requiring medical intervention (managed in an outpatient or inpatient setting) or sepsis as diagnosis in the hospitalization file whether access related or not.

Subject will be considered as having an infectious complication and will be counted as an event if the subject has experienced a device-related infection prior to the subject's end day of investigation period:

- **AE CRF Page:** Start Date of AE ≤ End Day of Investigation period **AND** Relationship to study Device: Equals 'Related' or 'Likely Related' **AND** Was event infectious: Equals Yes; subject will be considered as a failure at AE start date

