## KM Analysis

KM analysis will be used to estimate the time from the date of index procedure to the date of death and to determine the overall participant survival rate at 1-, 3-, 6-, and 12-months. Catheter-related death is considered as the event.

Subjects that have not reached catheter-related death (event) will be censored or considered event free as described below.

- If the subject has experienced following events, subject will be censored at the earliest date of those events.
  - Catheter has been removed due to Kidney Transplant, Transferred to AVG/AVF, Peritoneal Dialysis, Withdrawal of Care, or Other reasons
  - Subject has discontinued from the study.

Note: How to assess the above events has been described in **Error! Reference source not found.**the Binary Analysis section.

- All the other subjects will be considered event free and will be censored on visit day (visit day can vary from lower limit to upper limit of visit window).

This endpoint will be evaluated on the mITT population through 1-month, 3-months, 6-months, and 12-months.

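### If related events after a listed catheter removal are recorded, SAP 5.3.1, 5.3.2 and 5.3.4 count them while dropping event-free participants at that same removal

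*SAP*

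**What the plan says.** For freedom from device- or procedure-related adverse events (SAP 5.3.2, KM Analysis) the plan states: "Device and/or procedure-related adverse event is considered as the event". It then writes "Subjects that have not reached device and/or procedure-related adverse event will be censored or considered event free as described below". For those subjects, "If the subject has experienced following events, subject will be censored at the earliest date of those events", and the first such event is "Catheter has been removed due to Kidney Transplant, Transferred to AVG/AVF, Peritoneal Dialysis, Withdrawal of Care, or Other reasons"; the second is discontinuation. SAP 5.3.1 has the same structure for bloodstream infection ("Subjects that have not reached CRBSI (event) will be censored or considered event free as described below") and SAP 5.3.4 for death ("Subjects that have not reached catheter-related death (event) will be censored or considered event free as described below").

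The binary analyses in the same three sections work in the same order. A related event or catheter-related death up to the upper limit of the visit window is a failure. Only a subject who has not failed is then checked for a listed removal or discontinuation before the lower limit, which makes that subject non-evaluable.

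The primary endpoint differs. SAP 5.2.1 counts an adverse event only if "Start Date of AE ≤ End Day of Investigation period", and that period ends at a listed removal, at discontinuation, or at the 3-month cut-off, whichever is first.

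On follow-up after removal the documents disagree. SAP 2.6 and Protocol 7.2.1 say "Enrolled participants will continue clinical participation through the 12-month follow-up period" and do not mention removal. Protocol 7.5 keeps a participant in the study until follow-up is complete or until the day the catheter is removed.

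**The concern.** The sentence that opens the censoring rules selects subjects by whether they have the event, not by whether they have it before removal. Take two participants, both with a listed removal on day 40. One has a device-related adverse event on day 100; the other has none. Read literally, the first stays in the risk set to day 100 and is an event there, and the second leaves on day 40. Whether removal censors a participant then depends on what happens later. Kaplan-Meier estimation does not allow this, because those who stay after removal are exactly those who will fail.

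The resulting figure would not be freedom from the event while the catheter is in place, nor freedom through 12 months for everyone treated. Protocol section 3 and SAP 1.2 say the study's information is intended for the device's labeling, so a freedom rate with a 95% confidence interval should refer to a definable quantity.

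**Working it through.** **1. Does the text contain a cap at removal?** In the primary endpoint, yes (SAP 5.2.1). In the Kaplan-Meier paragraphs of 5.3.1, 5.3.2 and 5.3.4, no. In the matching binary rules, no: the only date limit on a failure is the upper end of the visit window. The Kaplan-Meier notes refer back to the binary sections for how to assess removal and discontinuation, so nothing there supplies the missing condition.

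**2. Can a post-removal event reach the data?** For: SAP 2.6 and Protocol 7.2.1 continue participation to 12 months; Protocol 7.4.1 asks at each visit how the participant has been dialyzed and wants session details only if the Pristine catheter is in use; Protocol 9.3 lets device-relatedness run to the completion of all follow-up. Against: Protocol 7.5 can end participation at removal, Protocol 8.1 collects nothing after discontinuation, and SAP section 7 ends adverse event collection at early termination. The passages are not reconciled.

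**3. Size if such events are recorded.** The plan states no expected rate or precision for these endpoints, so there is no figure to reproduce. Every rate below is an assumption. The only loss figure in the documents is 15% attrition through 90 days (SAP 2.4). Held at a constant hazard and treated as listed removal, it gives 1 − 0.85^(365/90) = 1 − 0.517 = 48% by 12 months.

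Let time run from 0 to 1 year, with in-place event hazard h = −ln(F), where F is in-place 12-month freedom; removal hazard g = −ln(0.517); and post-removal event hazard k = r × h. Under the literal rule:

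- event density: f(t) = h·e^(−(h+g)t) + k·I(t), where I(t) = ∫₀ᵗ g·e^(−(h+g)u)·e^(−k(t−u)) du
- risk set: Y(t) = e^(−(h+g)t) + I(t) − J(t), where J(t) = ∫₀ᵗ g·e^(−(h+g)u)·e^(−k(1−u)) du. The term I − J is the removed participants who will fail before 12 months, the only removed ones kept at risk
- literal estimate: exp(−∫₀¹ f/Y dt)
- censoring everyone at removal: F
- following everyone: e^(−(h+g)) + I(1)

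| In-place freedom F | r | Literal rule | Shift from F (points) | Everyone followed | Post-removal events per 142 |
|---|---|---|---|---|---|
| 0.70 | 0.1 | 0.690 | 1.0 | 0.768 | 1.2 |
| 0.70 | 0.25 | 0.675 | 2.5 | 0.755 | 3.0 |
| 0.70 | 1 | 0.616 | 8.4 | 0.700 | 10.8 |
| 0.85 | 0.1 | 0.844 | 0.6 | 0.885 | 0.6 |
| 0.85 | 0.25 | 0.836 | 1.4 | 0.879 | 1.5 |
| 0.85 | 1 | 0.798 | 5.2 | 0.850 | 5.6 |
| 0.90 | 0.1 | 0.896 | 0.4 | 0.924 | 0.4 |
| 0.90 | 0.25 | 0.890 | 1.0 | 0.920 | 1.0 |
| 0.90 | 1 | 0.863 | 3.7 | 0.900 | 3.7 |

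With r = 0, or with no post-removal event recorded, the literal rule equals F exactly. In every row above, the literal figure is below both alternatives. A simulation of 400,000 subjects at 47.7% removal agrees: 0.691, 0.676 and 0.620 for F = 0.70.

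**4. A force in the other direction.** Removal for infection or dysfunction is not on the censoring list, so such a participant can stay at risk to the visit day without a catheter. Adding 20% such removals by 12 months (assumed) to the F = 0.70 case, the simulated literal estimate is 0.735, 0.723, 0.703 and 0.673 at r = 0, 0.1, 0.25 and 0.5. Censoring at any removal gives about 0.70.

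**The case against.** The strongest reply is that the effect may never arise. Protocol 7.5 is the only passage that speaks directly to staying in the study after removal, and it can be read as ending participation that day. The sentences about continuing to 12 months are general. Listing removal and discontinuation separately may only reflect two case report form pages. This stands to the extent that the effect is conditional; it does not show that the conditional case is excluded.

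Second, not having reached the event can be read as not having reached it by the time of removal, which is ordinary Kaplan-Meier practice. Protocol Appendix A also lists access censoring events with no condition on what follows, and the derived-data specification (SAP Appendix 2) is listed but not in the public text. That reading is possible, but the binary rules give failure precedence and the SAP writes the cap out only for the primary endpoint.

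Third, the scope has limits. The infection definition in Protocol Appendix A calls for a culture from a catheter segment, so a new infection of that kind long after removal is unlikely. However, the case report form rule in SAP 5.3.1 asks only for a device-related bloodstream infection with clinical signs and a positive blood culture without apparent source. In SAP 5.3.5 the point has no force: a catheter already removed cannot be removed again.

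Fourth, a reader might infer that the reported rates are understated outright, by as much as 10 points. The documents do not support that. The effect is nil if nothing is recorded after removal, and step 4 shows that the net direction can reverse. A 10-point gap (80.0% against 90.5%) needs 78% listed removals and a related-event hazard of 0.10 per year both before and after removal.

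**Conclusion.** The point holds conditionally. As written, the Kaplan-Meier and binary rules in SAP 5.3.1, 5.3.2 and 5.3.4 have no condition placing the event on or before removal, unlike the primary endpoint. If post-removal events are recorded, the Kaplan-Meier estimate corresponds to no definable freedom rate, and from this cause alone it lies below the in-place value.

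With 48% listed removals and in-place freedom of 70% to 90%, the shift is about 0.5 to 2.5 points when the post-removal hazard is 0.1 to 0.25 times the in-place hazard, and about 3.5 to 8 points when it is unchanged. These sizes rest on constant hazards, on extrapolating 90-day attrition as removal, and on full recording after removal; the documents fix none of these. The secondary endpoints are descriptive, so no hypothesis test or success criterion changes. The case for acting is that the rates are meant for labeling and the correction is short.

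**What to change.** - **SAP 5.3.1 and 5.3.2, both analyses:** state that a subject is an event only if the event date is on or before the earliest of listed removal and discontinuation. Kaplan-Meier time is the earliest of event, listed removal, discontinuation and the time-point cut-off. Report related events that start after removal on a separate line. The binary rules must change with the Kaplan-Meier rules, or the two analyses of one endpoint would count different events.
- **SAP 5.3.4:** apply one rule to all participants. Either use the same ordering and report catheter-related deaths after removal separately, or do not censor at removal and follow everyone for death. Under the first option those deaths must stay visible and not simply drop out of the survival result.
- **Follow-up:** reconcile Protocol 7.5 with Protocol 7.2.1 and SAP 2.6 on whether follow-up continues after removal.

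The cost is a sentence or two in each analysis paragraph and a small change to the derivation code. The downside is small: post-removal events move from the curve to a separate line, and the adverse event tables in SAP section 7 would still hold any that are recorded.

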### **5.3.3 Rate of Technical Success, defined as the successful placement of the Pristine™ Long-Term Hemodialysis Catheter, as assessed by the Investigator during the Index Procedure.**

Subject will be considered as having technical success if the subject has experienced successful placement of the catheter at the intended site during the procedure:

- **Procedure Overview Part-1 CRF Page:** Was there successful placement at the intended site of the Pristine™ Long-Term Hemodialysis Catheter: Equals Yes

The rate of technical success will be reported with 95% confidence interval from the exact binomial method. The analysis will be performed on the ITT population.

### **5.3.4 Overall Participant Survival Rate at 1-month, 3-months, 6-months, and 12-months post-index procedure, defined as the proportion of participants that have not died from any catheter related complication.**

## Binary Analysis

Subject will be considered as a failure of the endpoint for a given visit if the subject has experienced the death due to a catheter-related complication prior to the upper limit of visit window for the visit:

- **Disposition-End of Study CRF Page:** Date of Death <= upper limit of the visit window  
**AND AE CRF Page:** Relationship to Device: Is 'Related' or 'Likely Related' AND Does the Event Meet the Definition of an SAE: Is Yes AND Results in Death: Is Yes and subject will be considered as a failure at the Death date

If the subject has not become failure and experience one of the following events prior to the lower limit of visit window, then subject will be considered as non-evaluable at the earliest occurrence of following event dates.

- Catheter has been removed due to Kidney Transplant, Transferred to AVG/AVF, Peritoneal Dialysis, Withdrawal of Care, or Other reasons
  - *Hemodialysis Catheter Re-Interventions CRF page: Catheter removal Equals Yes AND Reason for catheter removal Equals: Kidney Transplant, Transferred to AVG/AVF, Peritoneal Dialysis, Withdrawal of Care, or Other*

OR

- Subject has discontinued from the study.

If the subject has experienced any of the above non-evaluable events prior to the lower limit of visit window subject will be counted as a non-evaluable for a given visit. Else subject will be considered as a success of the endpoint for a given visit.

The overall participant survival rate will be reported with 95% confidence interval from the exact binomial method. The analysis will be performed on the mITT population through 1-month, 3-months, 6-months, and 12-months.

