2.3.1 Risk Assessment

The known possible risks associated with the use of the BD Pristine™ Long-Term Hemodialysis Catheter are listed below. The study involves only the collection of data, the only risk of taking part is the possible loss of confidentiality of your information collected in the study. None of the procedures or devices in this study are considered experimental.

Potential complications and Adverse Events (AEs) associated with the use of the Pristine™ Long-Term Hemodialysis Catheter may include the usual complications associated with central venous catheter procedures. These complications can occur singularly or collectively, and may include the following:

- Air Embolism
- Arterial Puncture
- Brachial Plexus Injury
- Cardiac Arrhythmia
- Cardiac Tamponade
- Catheter Erosion or Extrusion Through Skin
- Catheter Infection
- Catheter Occlusion or Breakage
- Catheter Thrombosis
- Catheter Tip Migration or Malposition
- Deep Vein Thrombosis – Lower Extremity
- Endocarditis
- Hemothorax
- Hydrothorax
- Inferior Vena Cava Injury
- Intolerance Reaction to Implanted Device
- Lower Extremity Ischemia
- Mediastinal Widening
- Pneumothorax
- Pulmonary Emboli
- Pulmonary Embolism
- Retroperitoneal Bleed
- Right Atrial Puncture
- Sepsis

- Exit Site Infection
- Exsanguination
- Extravasation
- Femoral Artery Damage
- Femoral Artery Dissection
- Femoral Nerve Damage
- Fibrin Sheath Formation
- Hematoma
- Hemorrhage
- Subclavian Artery Puncture
- Subcutaneous Tunnel Infection
- Superior Vena Cava Puncture
- Thoracic Duct Injury
- Thoracic Duct Laceration
- Thrombosis of Vein
- Trauma to major vessel or Right Atrium
- Tunnel Infection
- Venous stenosis

Table 1: Associated / Concomitant Procedures

Potential Risk of Clinical Significance	Summary of Data/Rationale for Risk	Mitigation Strategy
Associated / Concomitant Procedures		

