3.2 Secondary Endpoints

The following secondary endpoints will be evaluated using descriptive statistics to provide further information related to the safety and performance of the Pristine™ Long-Term Hemodialysis Catheter. All secondary endpoints will be summarized with descriptive statistics.

- *Rate of freedom from catheter-related bloodstream infection (CRBSI)*, defined by 2019 KDOQI Guidelines for CRBSI through 1-month, 3-months, 6-months, and 12 months post-index procedure.

- *Rate of freedom from Device and/or Procedure-related adverse events*, at 1-month, 3-months, 6-months, and 12 months post-index procedure.
- *Rate of Technical Success*, defined as the successful placement of the Pristine™ Long-Term Hemodialysis Catheter, as assessed by the Investigator during the Index Procedure.
- *Overall Participant Survival Rate* at 1-month, 3-months, 6-months, and 12 months post-index procedure, defined as the proportion of participants that have not died from any catheter related complication.
- *Overall Catheter Survival Rate* at 1-month, 3-months, 6-months, and 12 months post-index procedure, defined as the proportion of Pristine™ Catheters that have not been removed for any cause.
- *Overall Patency Rate*, at 1-month, 3-month, 6-months, and 12-months post-index procedure, defined as the Pristine™ catheter having the ability to achieve a mean dialysis blood flow of $\geq 300\text{mL/min}$ without need for additional interventions.^{5,6}

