9.3 Relationship of Adverse Event to Device(s)/Procedure

Each AE will be assessed for its relationship to the study device or procedure according to the following guidelines.

- A. Assess each AE for its relationship to the device or procedure.
 - Device Related: This category should be restricted to AEs directly attributable to the study device used from the placement procedure of the Pristine™ Catheter to completion of all follow-up for that patient.
 - Procedure Related: A procedure includes any study-related activity performed during the index procedure of the Pristine™ Catheter.
- B. The following categories shall be used for assigning the certainty of the relatedness.

Table 3: Relationship of Adverse Events

Relatedness	Description
Not Related	Event is independent of study intervention and/or evidence exists that the event is related to another etiology. There must be an alternative etiology documented by the clinician.
Unlikely Related	Event in which the temporal relationship to study intervention makes a causal relationship improbable (e.g., the event did not occur within a reasonable time of the study device use) and in which underlying disease provides plausible explanations (e.g., the participant's clinical condition other concomitant treatments).
Likely Related	Event in which there is evidence to suggest a causal relationship and the influence of other factors is less likely. The event occurs within a reasonable time after use of the study device and is less likely to be attributed to concurrent disease.
Related	Event in which there is clear evidence to suggest a causal relationship and other possible contributing factors can be ruled out. The event occurs in a plausible time relationship to use of the study device and cannot be explained by concurrent disease.

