### 2.7.2 Secondary Endpoints

The following secondary endpoints will be evaluated using descriptive statistics to provide further information related to the safety and performance of the Pristine™ Long-Term Hemodialysis Catheter. All secondary endpoints will be summarized with descriptive statistics.

- Rate of freedom from catheter-related bloodstream infection (CRBSI), defined by 2019 KDOQI Guidelines for CRBSI through 1-month, 3-months, 6-months, and 12-months post-index procedure.
- Rate of freedom from Device and/or Procedure-related adverse events, at 1-month, 3-months, 6-months, and 12 months post-index procedure.
- Rate of Technical Success, defined as the successful placement of the Pristine™ Long-term Hemodialysis Catheter, as assessed by the Investigator during the Index Procedure.
- Overall Participant Survival Rate at 1-month, 3-months, 6-months, and 12-months post-index procedure, defined as the proportion of participants that have not died from any catheter related complication.
- Overall Catheter Survival Rate at 1-month, 3-months, 6-months, and 12-months post-index procedure, defined as the proportion of Pristine™ Catheters that have not been removed for any cause.
- Overall Patency Rate, at 1-month, 3-month, 6-months, and 12-months post-index procedure, defined as the Pristine™ catheter having the ability to achieve a mean dialysis blood flow of  $\geq 300\text{mL/min}$  without need for additional interventions.

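### The participant-survival rule in SAP 5.3.4 does not count a death rated related to the placement procedure only, and its analysis set omits deaths before first dialysis

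*SAP*

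**What the plan says.** Protocol 3.2 lists Overall Participant Survival Rate as a secondary endpoint, "defined as the proportion of participants that have not died from any catheter related complication". Neither document says what makes a complication catheter-related.

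SAP 5.3.4 turns this into a rule. A participant fails at a visit if the date of death is on or before the upper limit of the visit window and the fatal event on the AE form satisfies "Relationship to Device: Is 'Related' or 'Likely Related' AND Does the Event Meet the Definition of an SAE: Is Yes AND Results in Death". A participant who has not failed, and who discontinued before the lower window limit, is non-evaluable. Everyone else is a success. The Kaplan-Meier version takes catheter-related death as the event, gives no wider definition, and censors participants at discontinuation. Both analyses use mITT only.

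SAP 5.3.2, for adverse events, adds a second route to failure: "OR Relationship to Procedure: Is 'Related' or 'Likely Related".

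Protocol 9.3 rates the two relationships separately. For device-related: "This category should be restricted to AEs directly attributable to the study device used from the placement procedure". For procedure-related: "Procedure Related: A procedure includes any study-related activity performed during the index procedure". Protocol 2.3.1 says that complications of using the catheter "may include the usual complications associated with central venous catheter procedures". Its list includes air embolism, cardiac tamponade, hemothorax and right atrial puncture.

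**The concern.** Some of the gravest harms of a tunneled catheter arise while it is being placed. An investigator who follows Protocol 9.3 may attribute a fatal vessel or cardiac injury to the procedure and not to the device. Under the SAP 5.3.4 rule that death is not a failure, and depending on its date it leaves the denominator or is scored as survival.

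The survival figure could then read 100% while the SAP 5.3.2 result includes a fatal procedure-related event. Protocol section 3 and SAP 1.2 say that the study's information is intended for the device labeling, so a one-sided rule in a mortality figure matters even where nothing is tested.

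**Working it through.** **1. How the rule classifies a death.** Appendix A of the protocol treats participant death as a form of premature discontinuation, so a death that does not meet the failure rule is read here as a discontinuation. The 1-month window is ±7 days; taking a month as 30 days, it runs from day 23 to day 37.

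| Death (all before the upper window limit) | Binary result in 5.3.4 | Kaplan-Meier |
|---|---|---|
| After first dialysis, rated device-related (procedure also or not) | Failure | Event |
| After first dialysis, rated procedure-related only, before the lower limit | Non-evaluable, leaves the denominator | Censored |
| After first dialysis, rated procedure-related only, between the lower and upper limits | Success at that visit, non-evaluable at later visits | Censored |
| Before first dialysis, any rating | Not in mITT | Not in mITT |

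The third row follows from the order of the clauses: a participant is non-evaluable only if the discontinuation precedes the lower limit, and all who remain are successes.

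The fourth row follows from SAP 4.1. The ITT set has three disposition groups, and participants with the device inserted but no first dialysis session form a different group from those treated with the study device. Only the treated group enters mITT.

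**2. Rule against endpoint.** The endpoint covers any complication that is catheter-related. Protocol 2.3.1 places the usual complications of central venous catheter procedures among those of this catheter. The rule admits only events rated against the device, so it is narrower than a natural reading of the endpoint.

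**3. Size (illustration).** The documents give no expected survival rate and no expected number of such deaths, so there is no planned figure to reproduce. Assume n = 142, the planned number with a catheter placed, all otherwise evaluable, and k procedure-only deaths after first dialysis and before the lower window limit. SAP 5.3.4 names the exact binomial interval. When all n survive, its lower 95% limit is 0.025^(1/n). For n = 141 this is 0.025^(1/141) = 0.974. Otherwise the limits for x survivors of n are the 2.5% quantile of Beta(x, n − x + 1) and the 97.5% quantile of Beta(x + 1, n − x).

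| k | As written | Deaths counted |
|---|---|---|
| 1 | 141/141 = 100% (97.4 to 100) | 141/142 = 99.3% (96.1 to 99.98) |
| 2 | 140/140 = 100% (97.4 to 100) | 140/142 = 98.6% (95.0 to 99.8) |
| 3 | 139/139 = 100% (97.4 to 100) | 139/142 = 97.9% (94.0 to 99.6) |

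Each uncounted death is worth 1/142 = 0.7 percentage points. If the single death falls inside the window instead, the result at that visit is 142/142 = 100% (97.4 to 100), with the dead participant counted as a survivor.

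**The case against.** A reader might infer that a placement death can never be a failure. The documents do not support that. Device and procedure relationship are separate ratings, and one event can carry both. Protocol 9.1.3 includes events arising from deployment, implantation and user error among adverse device effects, and the device-related category in Protocol 9.3 runs from the placement procedure onward. A fatal placement injury may be rated device-related, and if the participant is in mITT it then counts. The gap concerns deaths rated against the procedure only, and how often investigators would rate that way is unknown.

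A reader might also infer that 5.3.4 contradicts 5.3.2. It does not. The endpoint in 5.3.2 is named "Rate of freedom from Device and/or Procedure-related adverse events, at 1-month, 3-months, 6-months, and 12 months post-index procedure", so its rule has to include procedure. The SAP's rules for infectious complications, non-infectious complications and CRBSI also use device relationship alone. SAP 5.3.2 serves only as precedent: it shows that both fields are on the AE form.

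It can fairly be said that such a death would be visible elsewhere: in 5.3.2 on ITT through 1 month, in the SAP section 7 tables of adverse events by relationship to procedure, in the listings, and in disposition by reason for discontinuation. The endpoint is descriptive and carries no test. All of this stands and lowers the priority. It does not correct the survival figure, and SAP section 7 specifies no table of deaths by relationship.

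Finally, a procedure clause alone would miss deaths before first dialysis. That is correct, and is why the population must change as well.

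**Conclusion.** The point holds in a limited form. As written, a death rated related to the placement procedure only cannot be a failure in SAP 5.3.4, and a death before first dialysis is not analyzed under any rating. Both omissions favor the device. A placement death rated device-related in a participant who has reached first dialysis is counted.

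The effect is about 0.7 percentage points per uncounted death, assuming 142 participants; the number of such deaths cannot be predicted from the documents. The classification rests on two readings: that death counts as discontinuation, as Appendix A of the protocol indicates, and that the group without a first dialysis session is excluded from mITT, as the disposition groups in SAP 4.1 indicate. Priority is low to moderate: no test or decision depends on this endpoint, but it is a safety figure from a study whose results are intended for labeling.

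**What to change.** In SAP 5.3.4, for both the binary rule and the Kaplan-Meier event:

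- Define catheter-related death as a fatal SAE rated Related or Likely Related to the device or to the procedure.
- Count such a death as a failure at every visit whose upper window limit falls on or after the date of death, so that none is classed as non-evaluable or as a success.
- Add a 1-month result on the SAP's ITT set, as 5.3.2 already does, so that deaths before first dialysis are included. State how ITT participants are handled when their follow-up is limited: Protocol 7.2.1 ends participation at the index procedure if the catheter was not introduced, and Protocol 7.4.1 limits collection to 30 days if it was introduced without procedure success.

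The cost is one clause and one additional 1-month row. Both relationship fields are already on the AE form, so no new variable is needed. The only downside for the sponsor is that the reported rate can become slightly less favorable and never more so.
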